3.1 Primary

The primary objective of this study is to compare overall survival of patients with advanced colorectal cancer who are refractory to all available therapy treated with durvalumab and tremelimumab combined with best supportive care to the overall survival of patients treated with best supportive care alone.

3.2 Secondary

Secondary objectives are to:

- Compare progression-free survival (PFS) between the two treatment arms.
- Compare objective response rates (ORR) between the two treatment arms.
- Assess the toxicity and safety profile of the combination of durvalumab and tremelimumab and best supportive care.

4. Endpoints

4.1 Primary Efficacy

The primary efficacy endpoint is overall survival.

4.2 Secondary Efficacy

The secondary efficacy endpoints are progression-free survival and objective response rate.

4.3 Safety

The safety endpoints are serious and non-serious adverse events (clinical and laboratory), laboratory parameters, dosing data (including dose interruptions, total delivered dose and dose modifications) and reasons off treatment.

5. Sample Size and Power

The primary objective of this study is to assess the additional effect of durvalumab and tremelimumab to best supportive care by comparing overall survival (OS) between Durva+Treme and BSC arms among all randomized patients. It was calculated that with a 2-sided alpha of 10%, a total of 180 patients with 150 events (deaths) would be required to provide 80% power to detect a 2.4 month difference in median survival (a hazard ratio of 0.65) between the two treatment arms assuming a median survival of 4.5 months for the BSC alone arm. The final analysis will be conducted after at least 150 events have been recorded. It is estimated that 180 patients accrued over 18 months and followed for 6 months will be required to reach the necessary number of events.

6. Data Set Descriptions

Three types of analysis samples will be used:

All Randomized Patients:

All patients who have been randomized in the study with the treatment arm being as randomized.

Response-Evaluable Patients:

All patients who have received at least one cycle of therapy and have their disease re-evaluated will be considered evaluable for response (exceptions will be those who exhibit objective disease progression prior to the end of cycle 1 who will also be considered evaluable).

All Treated Patients:

All patients on Durva+Treme who received at least one dose of durvalumab and tremelimumab and on BSC who had at least one Best Supportive Care Report.

Patients randomized to BSC who have received at least one dose of durvalumab and tremelimumab on study (from Cancer Treatment Section of Best Supportive Care Report) will be grouped with patients randomized to Durva+Treme in analyses of safety.

7. Statistical Analysis

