7.1 Protocol Treatment Plan

7.1.1 Drug Administration

Patients will be randomized at a 2:1 ratio to receive durvalumab plus tremelimumab plus best supportive care or best supportive care only to a planned sample size of 180.

Best supportive care is defined as those measures designed to provide palliation of symptoms and improve quality of life as much as possible.

When durvalumab is given with tremelimumab, tremelimumab will be administered first. Durvalumab will start immediately after the tremelimumab infusion (during the post-tremelimumab observation period).

One cycle will be defined as 28 days (4 weeks). Study drugs will be started on cycle 1. Tremelimumab will only be given for the first 4 cycles.

| Arm | Agent(s) | Dose | Route | Duration* (infusion) | Schedule |
|-----|----------------------|---------|-------|----------------------|---------------------|
| 1 | Best Supportive Care | NA | NA | NA | NA |
| 2 | Tremelimumab | 75 mg | IV | 60 minutes | Day 1, cycles 1-4 |
| | Durvalumab | 1500 mg | IV | 60 minutes | Day 1 every 28 days |
| | Best Supportive Care | NA | NA | NA | NA |

* Duration (overall) of durvalumab and tremelimumab is until unequivocal progression or unacceptable toxicity.

Arm 2: DURVALUMAB and TREMELIMUMAB

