9.1.1 Durvalumab +/- Tremelimumab Adverse Events of Special Interest

An adverse event of special interest (AESI) is one of scientific and medical interest specific to understanding of the Investigational Product and may require close monitoring. An AESI may be serious or non-serious.

AESIs for durvalumab ± tremelimumab include, but are not limited to events with a potential inflammatory or immune-mediated mechanism and which may require more frequent monitoring and/or interventions such as steroids, immunosuppressants and/or hormone replacement therapy. **These AESIs may require close monitoring in the treatment arms with durvalumab ± tremelimumab.**

An immune-mediated adverse event (imAE) is defined as an AESI that is associated with drug exposure and is consistent with an immune-mediated mechanism of action and where there is no clear alternate etiology. Serologic, immunologic, and histologic (biopsy) data, as appropriate, should be used to support an imAE diagnosis. Appropriate efforts should be made to rule out neoplastic, infectious, metabolic, toxin, or other etiologic causes of the imAE.

If the Investigator has any questions in regards to an event being an imAE, the Investigator should promptly contact the CCTG.

AESIs observed with durvalumab ± tremelimumab include:

- Diarrhea / Colitis, and intestinal perforation;
- Pneumonitis / Interstitial Lung Disease (ILD);
- ALT/AST increases / hepatitis / hepatotoxicity;
- Neuropathy / neuromuscular toxicities (e.g. Guillain-Barré syndrome, and myasthenia gravis);
- Endocrinopathies (i.e. events of hypophysitis, hypopituitarism, adrenal insufficiency, diabetes insipidus, hyper- and hypothyroidism and type I diabetes mellitus);
- Rash / Dermatitis;
- Nephritis / Blood creatinine increases;
- Pancreatitis (or labs suggestive of pancreatitis - increased serum lipase , increased serum amylase);
- Myocarditis;
- Myositis/polymyositis
- Other inflammatory responses that are rare with a potential immune-mediated aetiology include, but are not limited to, pericarditis, sarcoidosis, uveitis and other events involving the eye, skin, hematological and rheumatological events.

In addition, infusion-related reactions and hypersensitivity/anaphylactic reactions with a different underlying pharmacological etiology are also considered AESIs.

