Progression-Free Survival (PFS) is defined as the time from randomization to the first objective documentation of disease progression or death due to any cause. If a patient has not progressed or died at the time of final analysis, PFS will be censored on the date of the last tumour assessment. This includes patients who are lost to follow-up or have withdrawn consent. All analyses for OS will also be performed for PFS, using similar methodology. A sensitivity analysis of PFS will also be performed where PFS is defined as the time from randomization to the second documentation of unequivocal disease progression in those patients who continued study therapy beyond the first objective documentation of disease progression and with interim CR, PR or SD documented.

Objective Response Rate:

Objective Response Rate (ORR) is defined as the proportion of patients with a documented complete response and partial response based on RECIST 1.1. The primary estimate of ORR will be based on all patients randomized. A Cochran-Mantel-Haenszel test adjusting for the stratification factors (ECOG performance status, site of tumour) at the time of randomization will be used to compare the objective response rates between two arms. A sensitivity analysis of ORR will also be performed where response is defined as the proportion of patients with a documented complete response and partial response based on RECIST 1.1 and/or Immune-Related Response Criteria (irRC) [Wolchok 2009].

Safety Analysis:

All patients who have received at least one dose of protocol treatment will be included in the safety analysis. The incidence of adverse events will be summarized by type of adverse event and severity using the NCI Common Terminology Criteria for Adverse Events. A Fisher's exact test will be used to compare adverse events between the two arms if required.

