| Severity Grade of the Event (NCI CTCAE version 4.03) | Dose Modifications | Toxicity Management |
|--|---|---|
| Any Grade | General Guidance | For Any Grade: |
| | 
 - Manage per institutional standard at the discretion of investigator. - Monitor patients for signs and symptoms of infusion-related reactions (e.g., fever and/or shaking chills, flushing and/or itching, alterations in heart rate and blood pressure, dyspnea or chest discomfort, or skin rashes) and anaphylaxis (e.g., generalized urticaria, angioedema, wheezing, hypotension, or tachycardia). | 
 - Manage per institutional standard at the discretion of investigator. - Monitor patients for signs and symptoms of infusion-related reactions (e.g., fever and/or shaking chills, flushing and/or itching, alterations in heart rate and blood pressure, dyspnea or chest discomfort, or skin rashes) and anaphylaxis (e.g., generalized urticaria, angioedema, wheezing, hypotension, or tachycardia). |
| Grade 1 or 2 | For Grade 1: | For Grade 1 or 2: |
| | 
The infusion rate of study drug/study regimen may be decreased by 50% or temporarily interrupted until resolution of the event.
 | 
 - Acetaminophen and/or antihistamines may be administered per institutional standard at the discretion of the investigator. - Consider premedication per institutional standard prior to subsequent doses. - Steroids should not be used for routine premedication of Grade ≤2 infusion reactions. |
| | For Grade 2: | |
| | 
The infusion rate of study drug/study regimen may be decreased 50% or temporarily interrupted until resolution of the event.
 
Subsequent infusions may be given at 50% of the initial infusion rate.
 | |
| Grade 3 or 4 | For Grade 3 or 4: | For Grade 3 or 4: |
| | 
Permanently discontinue study drug/study regimen.
 | 
 - Manage severe infusion-related reactions per institutional standards (e.g., IM epinephrine, followed by IV diphenhydramine and ranitidine, and IV glucocorticoid). |

CTCAE Common Terminology Criteria for Adverse Events; IM intramuscular; IV intravenous; NCI National Cancer Institute.

Non-Immune-Mediated Reactions

| Severity Grade of the Event (NCI CTCAE version 4.03) | Dose Modifications | Toxicity Management |
|---|---|---|

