7.5 Extent of Exposure to Durvalumab and Tremelimumab

Patients included are those who received at least one dose of durvalumab or tremelimumab as defined in Section 6.

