7.7 Safety

The safety analyses will be based on the All Treated population defined in Section 6. Adverse events and laboratories are graded and categorized using the CTCAE v4.0 criteria except where CTCAE grades are not available.

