...	** (**)	** (**)	** (**)	** (**)	** (**)	** (**)
** (**)	** (**)	** (**)	** (**)	** (**)	** (**)	** (**)

(a) Patients may have more than one event within a category.

(3) Related to Durvalumab or Tremelimumab

Data set: All Treated Patients on DURVA+TREME Arm						
	Number of patients (%) N=***					Any grade
	Worst grade					
	1	2	3	4	5	
	** (**)	** (**)	** (**)	** (**)	** (**)	** (**)
Patients with AE related to Tremelimumab within category						
Category 1 ^(a)						
Event 1	** (**)	** (**)	** (**)	** (**)	** (**)	** (**)
Event 2	** (**)	** (**)	** (**)	** (**)	** (**)	** (**)
Event 3	** (**)	** (**)	** (**)	** (**)	** (**)	** (**)
...	** (**)	** (**)	** (**)	** (**)	** (**)	** (**)
Category 2 ^(a)						
Event 1	** (**)	** (**)	** (**)	** (**)	** (**)	** (**)
...	** (**)	** (**)	** (**)	** (**)	** (**)	** (**)

(a) Patients may have more than one event within a category.

(4) Related to Both Durvalumab and Tremelimumab

Data set: All Treated Patients on DURVA+TREME Arm						
	Number of patients (%) N=***					Any grade
	Worst grade					
	1	2	3	4	5	
	** (**)	** (**)	** (**)	** (**)	** (**)	** (**)
Patients with AE related to Tremelimumab within category						
Category 1 ^(a)						
Event 1	** (**)	** (**)	** (**)	** (**)	** (**)	** (**)
Event 2	** (**)	** (**)	** (**)	** (**)	** (**)	** (**)
Event 3	** (**)	** (**)	** (**)	** (**)	** (**)	** (**)
...	** (**)	** (**)	** (**)	** (**)	** (**)	** (**)
Category 2 ^(a)						
Event 1	** (**)	** (**)	** (**)	** (**)	** (**)	** (**)
...	** (**)	** (**)	** (**)	** (**)	** (**)	** (**)

(b) Patients may have more than one event within a category.

Table 45: Overall Adverse Events

Data set: All Treated Patients on DURVA+TREME Arm						
	Number of patients (%)					Any grade
	N=***					
	Worst grade					
	1	2	3	4	5	
Patients with any AE	** (**)	** (**)	** (**)	** (**)	** (**)	** (**)
Patients with AE within category						
Category 1 ⁽¹⁾	** (**)	** (**)	** (**)	** (**)	** (**)	** (**)
Event 1	** (**)	** (**)	** (**)	** (**)	** (**)	** (**)
Event 2	** (**)	** (**)	** (**)	** (**)	** (**)	** (**)
Event 3	** (**)	** (**)	** (**)	** (**)	** (**)	** (**)
...						
Category 2 ⁽¹⁾	** (**)	** (**)	** (**)	** (**)	** (**)	** (**)
Event 1	** (**)	** (**)	** (**)	** (**)	** (**)	** (**)
...						

(1) Patients may have more than one event within a category.

Note: The same type of table will be made for BSC arm.

Table 46: Severe Overall Adverse Events

Data set: All Treated Patients						
	Number of patients (%)					

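### SAP Section 6 admits Arm 2 patients to the safety set only if they received durvalumab and tremelimumab; the protocol and SAP 7.5 require any dose of either

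*SAP*

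**What the plan says.** SAP Section 6 (Data Set Descriptions) defines All Treated Patients as "All patients on Durva+Treme who received at least one dose of durvalumab and tremelimumab and on BSC", with BSC patients entering once they have at least one Best Supportive Care Report. SAP 7.7 then ties safety to that definition: "The safety analyses will be based on the All Treated population defined in Section 6".

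Other places state a different rule:

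- Protocol 13.2, Safety Analysis: "All patients who have received at least one dose of protocol treatment will be included in the safety analysis".
- Protocol 8.1.1 makes patients evaluable for adverse events from their first treatment.
- SAP 7.5 on exposure: "Patients included are those who received at least one dose of durvalumab or tremelimumab as defined in Section 6". It refers back to Section 6 but uses the other conjunction, and SAP 7.5.1 uses *or* again.

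Section 6 also regroups BSC patients who received study drug with Arm 2 for safety, and that sentence has the same *and*.

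**The concern.** A population definition decides who is counted, and here the SAP's definition is narrower than the protocol's. Read literally, an Arm 2 patient who received one drug but not the other is not in the safety set. Toxicity is a secondary objective, and under this reading whether a dosed patient is counted can depend on toxicity during the first infusion.

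The exclusion would also be one-sided. Nothing comparable removes a BSC patient for early toxicity, and SAP 7.7.1 compares overall adverse events between the arms with Fisher's exact test.

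**Working it through.** **Which reading do the documents support?**

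For *or* as the intended meaning:

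- SAP 7.5 and 7.5.1 use *or*, the former while citing Section 6.
- Protocol 13.2 counts any dose of protocol treatment.
- The SAP often uses the two drug names joined by *and* simply as the regimen's name, as in SAP 7.7.4.
- Table 27 gives a separate N for each drug. If every patient in the set had received both drugs, the two Ns would always be equal.

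For the literal *and* remaining open to a programmer:

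- Table 44 has one part headed "Related to Durvalumab or Tremelimumab" and another for events related to both drugs, so the SAP does separate the two ideas.
- Table 6 has separate rows for both drugs, durvalumab only and tremelimumab only, so one-drug patients were foreseen.

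**Can a one-drug patient arise?** Protocol 7.1.1 fixes the order: "When durvalumab is given with tremelimumab, tremelimumab will be administered first". For a Grade 3 or 4 infusion-related reaction, Appendix III says "Permanently discontinue study drug/study regimen". If that stops the whole regimen during the first tremelimumab infusion, the patient never receives durvalumab. Protocol 9.1.1 gives such events particular weight: "infusion-related reactions and hypersensitivity/anaphylactic reactions with a different underlying pharmacological etiology are also considered AESIs".

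**What would that patient be missing from?** Under the literal reading: the adverse event tables, the laboratory tables, Table 57 (deaths on or within 4 weeks of treatment) and Table 58 (adverse events leading to discontinuation). The exposure tables (23 to 31) carry the same data set label and inherit the ambiguity. The patient would still appear in Table 6, and SAE reporting is unaffected. Immune toxicity that appears after both drugs have been given is also unaffected.

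**Size.** The plan gives no figure on this point to reproduce. Inputs:

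- Planned Arm 2 size: 180 × 2/3 = 120, as stated in SAP 2.1.
- Assumption: all 120 are dosed.
- Assumption: exactly one of them received one drug only.
- Assumption: m of the other 119 had a given event.

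One patient is 1/120 = 0.83% of the arm.

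If the excluded patient had the event, the correct rate is (m+1)/120 and the reported rate is m/119:

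(m+1)/120 − m/119 = (119 − m)/14280

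| m | Reported | Correct | Too low by (points) |
|---|---|---|---|
| 0 | 0% | 0.83% | 0.83 |
| 5 | 4.20% | 5.00% | 0.80 |
| 10 | 8.40% | 9.17% | 0.76 |
| 30 | 25.21% | 25.83% | 0.62 |

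If the excluded patient did not have the event, the reported rate is too high by m/119 − m/120 = m/14280, which is 0.07 points at m = 10 and 0.21 points at m = 30.

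With no one-drug patients the difference is zero.

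**The case against.** The strongest reply is that the SAP answers the question itself. SAP 7.5 says what Section 6 means, the exposure and safety tables for Arm 2 carry the same data set label, and the protocol agrees. Where the SAP wants the conjunction, in Tables 6 and 44, it writes *both*, which Section 6 does not. Table 44 is also weak evidence of careful wording, because parts 3 and 4 reuse a row label from part 2. On this view the point is a copy-edit.

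The route to a one-drug patient can be challenged too. The Appendix III wording does not say outright whether a reaction during tremelimumab stops one drug or both, and Tables 31 and 58 record discontinuation drug by drug. The window is short, because durvalumab follows directly after a 60-minute tremelimumab infusion.

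Much of this stands. *Or* is the likely intent, the numbers are likely small, and the route depends on reading Appendix III as stopping the whole regimen, which is a fair reading but not the only one. What does not follow is that nothing needs changing. Section 6 is the definition that SAP 7.7 cites, and as worded it conflicts with protocol 13.2. A programmer who follows it exactly would produce a different safety set, and Table 6 shows that the affected category was foreseen.

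**Conclusion.** The concern holds. The Arm 2 All Treated definition is wrong as written: it conflicts with protocol 13.2 and with the SAP's own reference to it in 7.5. The conflict in wording is certain. Actual exclusion of a patient requires both that a one-drug Arm 2 patient exists and that *and* is programmed literally.

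In common event rates the effect of one such patient is well under one percentage point. It matters most for a rare, serious reaction: if the excluded patient is the only case, the table shows none. OS, PFS and ORR use all randomized patients, so they, the sample size and the power are untouched.

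**What to change.** In SAP Section 6, define All Treated on Arm 2 as patients who received any amount of at least one dose of durvalumab *or* tremelimumab. This matches protocol 13.2 and SAP 7.5, and the exposure and safety tables then share one definition.

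In the BSC regrouping sentence, the sponsor should state whether a BSC patient who received only one study drug is moved to Arm 2 for safety. Protocol 13.2 does not settle that question.

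The cost is a small wording change to the Arm 2 definition and one clarifying phrase for BSC. No new data are needed, and no dosing or stopping rule changes.

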
5.3 Follow-up for Ineligible Patients

The follow-up requirements for ineligible patients:

- Randomized to **Arm 1** (BSC) include submission of the Baseline Report plus annual follow-up using the Minimal Follow-up Report.
- Randomized to **Arm 2** (tremelimumab and durvalumab) but who have received no protocol therapy include submission of the Baseline Report plus annual follow-up using the Minimal Follow-up Report. Data submission for ineligible participants who have received at least one dose of protocol therapy should be followed according to the protocol to allow for treatment and adverse event assessment.

Note: The dates of objective progression and death must be reported for ineligible patients.

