7.0 TREATMENT PLAN

Although the Canadian Cancer Clinical Trials Group acts as the coordinating agency for the trial, the responsibility for the treatment of patients rests with each individual investigator.

In accordance with CCTG policy, protocol treatment is to begin within 2 working days of patient randomization.

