APPENDIX IV - DOCUMENTATION FOR STUDY

Follow-up is required for patients from the time of randomization and will apply to all eligible patients.

This trial will use a web-based Electronic Data Capture (EDC) system for all data collection. For details of accessing the EDC system and completing the on-line Case Report Forms please refer to the “CCTG EDC Generic Data Management Guidebook” posted on the CO.26 area of the CCTG web-site (www.ctg.queensu.ca).

The electronic CRFs to be used in this trial, through the EDC system, are as follows:

| Electronic Folder | Timing | To be completed electronically | Supporting Documentation Required ¹ |
|---|--|--|--|
| Eligibility Checklist | | At the time of randomization | 
 • consent form² |
| Baseline Report | | Within 2 weeks of randomization | 
 • relevant pathology report(s) • RAS reports • relevant operative report(s) • relevant radiology reports (including CT/MRI abdomen/pelvis, CT/MRI chest, chest x-ray) • tumour measurement worksheet • ECG report |
| Correlative Studies Report (Tumour and Blood) | Continuous running-log folder See Section 5.0 | Information pertaining to tumour tissue submission must be completed as soon as possible after randomization, and tissue submitted within 4 weeks of randomization. | 
 • Consent form² • Diagnostic pathology report (for tumour tissue only) |
| | | Information pertaining to baseline/pretreatment blood collection for correlative studies (i.e. whole blood, plasma, serum) must be completed within 2 weeks of randomization. | |
| | | Information pertaining to post randomization blood collection samples (i.e. whole blood, plasma, serum) for correlative studies and banking should be completed within 2 weeks after collection of blood specimens. | |
| Concomitant Medication Report | Continuous running-log folder | | |
| Best Supportive Care Report (Arm 1 only) | Every 4 weeks (28 days) until objective progression | Within 2 weeks of the end of each reporting period | 
 • If available/applicable: • CT/MRI abdomen/pelvis report • CT/MRI chest • other radiology reports • tumour measurement worksheet • ECG report |

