7.7.1 Adverse Events

Adverse events will be recorded on the CCTG toxicity/adverse event-intercurrent illness case report form. Events reported on Treatment Report or 4-Week Post-Treatment Follow-Up Report for patients on the Durva+Treme arm will be defined as adverse events on Durva+Treme; Events reported on any case report forms except Form 1 will be summarized separately for patients on both arms as overall adverse events during the (whole) study.

Drug related adverse events are those events with a relation to protocol therapy of 3=possible, 4=probable or 5=definite.

Severe adverse events are those events reported with a CTCAE Grade of 3 or higher.

Comparisons between treatment arms on overall adverse events (any vs. other, severe vs. other) will be carried out using a two sided Fisher's exact test at an alpha level of two-sided 10%.

The following variables are summarized. Tabulations of overall adverse events will be presented by treatment group.

- Adverse events on Durva+Treme: worst CTCAE grade per patient (**Table 42**)
- Severe adverse events on Durva+Treme: worst CTCAE grade per patient (**Table 43**)
- Drug related adverse events on Durva+Treme: worst CTCAE grade per patient (**Table 44**)
- Overall adverse events: worst CTCAE grade per patient (**Table 45**)
- Severe overall adverse events: worst CTCAE grade per patient (**Table 46**)

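### The safety set admits Arm 2 patients on dosing but BSC patients only if a Best Supportive Care Report exists, so BSC patients can drop out of the adverse-event comparison in one arm only

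*SAP*

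**What the plan says.** SAP Section 6 defines the All Treated set differently by arm. For Arm 2 it is "All patients on Durva+Treme who received at least one dose of durvalumab and tremelimumab". For the control arm it is those "on BSC who had at least one Best Supportive Care Report". SAP 7.7 then states: "The safety analyses will be based on the All Treated population defined in Section 6". SAP 7.7.1 compares any and severe overall adverse events between arms by Fisher's exact test at two-sided 10%.

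The control-arm form is scheduled in Protocol Appendix IV as "Every 4 weeks (28 days) until objective progression", to be completed within two weeks of the end of each period. Arm 2 patients qualify almost at once, because "protocol treatment is to begin within 2 working days of patient randomization".

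For ineligible patients, the Arm 1 bullet of Protocol 5.3 reads in part "BSC) include submission of the Baseline Report plus annual follow-up using the Minimal Follow-up Report". The Arm 2 bullet has ineligible patients with at least one dose followed per protocol so that adverse events can be assessed.

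The safety paragraph of Protocol 13.2 says "All patients who have received at least one dose of protocol treatment will be included in the safety analysis". It gives no entry rule for BSC patients, yet allows a between-arm Fisher test if required.

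**The concern.** In Arm 2 a patient enters the safety set through a treatment event within days of randomization. In the BSC arm a patient enters through the existence of a form that covers 28 days. Two kinds of BSC patient can fail to qualify: those found ineligible before a first report is filed, and those who die before the first period ends if the site files nothing for the part period. Their Arm 2 counterparts stay in once dosed.

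Early deaths are likely to carry more severe adverse events than other patients. Losing them from the BSC numerator and denominator would lower the BSC severe-event rate and make Arm 2 look more toxic by comparison. There is little back-up: Protocol 9.1 does not require SAE reporting for BSC patients. SAP 7.7.1 does accept events from any post-baseline form, but by then SAP Section 6 has already excluded the patient. Protocol 13.1 lists the between-arm adverse-event comparison among the secondary objectives, so the denominator matters.

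**Working it through.** **Design figure.** Inputs from Protocol 13.3: HR 0.65, two-sided alpha 10%, power 80%; 2:1 allocation from Protocol 13.1. Schoenfeld events = (1.645 + 0.842)² / [(ln 0.65)² × (2/3) × (1/3)] = 6.18 / (0.1856 × 0.2222) = 150, as stated. This figure is not in question, because overall survival uses all randomized patients.

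**Ineligible BSC patients.** This is a matter of text. Protocol 5.3 asks them only for the Baseline Report and annual Minimal Follow-up Reports. SAP Section 6 requires a Best Supportive Care Report. A BSC patient found ineligible before filing one is therefore excluded by following the documents. The number is not given.

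**Early deaths.** Assume exponential survival with medians of 4.5 and 6.9 months (Protocol 13.3), arms of 60 and 120 (SAP 2.1), and 28 days = 28/30.4375 = 0.920 months.
- BSC: 1 − exp(−ln 2 × 0.920/4.5) = 13.2%, or 7.9 of 60.
- Arm 2: 1 − exp(−ln 2 × 0.920/6.9) = 8.8%, or 10.6 of 120, nearly all kept because dosing has begun.
- With a BSC median of 6 months (Protocol 2.0 cites 5-6 months), the BSC figure is 10.1%, or 6.1 of 60.

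These are upper-end figures. The same model puts 1 − exp(−ln 2 × 2.76/4.5) = 35% of BSC patients dead by 12 weeks, while criterion 4.1.12 requires a life expectancy of at least 12 weeks.

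**Effect on the BSC rate.** Assume severe-event rates of 80% in early deaths and 35% in others. Neither rate is in the documents. The full BSC rate is 0.132 × 0.80 + 0.868 × 0.35 = 40.9%. If every early death is lost it is 35.0%, about 6 points lower.

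**Effect on the Fisher test.** I simulated 20,000 trials per cell, with the same 80%/35% risks in both arms and rejection at p ≤ 0.10. The entries are the percentage of trials rejecting, with rejections showing more toxicity in Arm 2 in brackets. Simulation error is about 0.2-0.3 points.

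| Early deaths, BSC / Arm 2 | No BSC early death lost | Half lost | All lost |
|---|---|---|---|
| 13.2% / 8.8% (design) | 9.5 (2.2) | 8.3 (5.0) | 12.0 (10.7) |
| 13.2% / 13.2% (equal) | 7.8 (3.7) | 10.0 (8.0) | 16.6 (15.8) |
| 6% / 4% (assumed) | 8.6 (2.9) | 8.5 (4.4) | 9.5 (6.5) |

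In the first and third rows Arm 2 has fewer early deaths and so a slightly lower true severe-event rate (design row: 39.0% against 40.9%), which works against the bias. With the design early-death rates, all early deaths lost, and severe-event rates of 60-80% in early deaths and 25-35% in others, rejection runs from about 10% to 14%.

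**Single-trial illustration (assumed counts).** Severe events in 60/120 against 24/60 give p = 0.27. Dropping BSC patients who all had a severe event gives 22/58, p = 0.15 (2 dropped); 20/56, p = 0.104 (4 dropped); and 16/52, p = 0.029 (8 dropped).

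**The case against.** The early-death route is inferred. The Best Supportive Care Report is a period report and does not depend on attending a week-4 visit. The Arm 2 Treatment Report has the same 4-weekly timing, and nobody would assume that it is missing for a patient who dies in week 3. Protocol 5.1 has BSC adverse events evaluated continuously, and Protocol 6.3 has all randomized patients followed to death. A loss of zero is as compatible with the documents as a loss of all. This stands, and it is why the size is unknown.

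Three stronger readings are tempting but not supported.
- A reader might infer that BSC patients dying before week 4 are excluded. No text says that death cancels the first report.
- A reader might take the Never Treated row for BSC in SAP Table 1 as made for such deaths. The row is generic, covers both arms, and could equally hold immediate withdrawals.
- A reader might quote 16-17% as the error rate. That needs every early death lost and equal early mortality in both arms, which differs from the design's own 13.2% and 8.8%.

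It is also fair that no decision rule rests on this test, that Protocol 13.2 plans it only if required, and that strict eligibility checks should keep ineligible patients few. Against that, SAP 7.7.1 plans the comparison without condition, and none of these points removes the asymmetry in Protocol 5.3.

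**Conclusion.** The concern holds in a limited form. The entry rules differ by arm. For BSC patients found ineligible before a first report, exclusion follows from the documents as written. For early BSC deaths it is possible but not established.

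The bias overstates excess Arm 2 toxicity if those lost had more severe events. Under the 80%/35% assumption, Fisher rejection at nominal 10% is about 12% with complete loss at the design hazards, 16-17% with complete loss and equal early mortality, and about 8-10% with half lost. Overall rejection therefore clearly exceeds nominal only when most early deaths are lost, although rejections shift towards apparent Arm 2 harm sooner. All of this rests on an assumed share of missing reports, assumed severe-event rates and an exponential model that probably gives too many early deaths. Overall survival is untouched. Minor to moderate.

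**What to change.** - **SAP Section 6:** define the BSC safety set as all patients randomized to BSC, except those who withdrew consent before any post-randomization follow-up.
- **Protocol 5.3 and Appendix IV:** require one Best Supportive Care Report for every BSC patient, covering randomization to death, ineligibility or progression, including part periods.
- **SAP 7.7:** tabulate BSC patients with no adverse-event data by reason, and do not count them as event-free.
- **Protocol 13.2:** align the safety population with this definition, so that it states a rule for BSC patients.

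The report is essential. Nothing in the documents shows adverse-event fields on the Death or Minimal Follow-up Reports, so widening the denominator alone would push the BSC rate down. The cost is SAP and protocol wording and one extra existing form for a few BSC patients.
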